Three main factors affect patients' cardiopulmonary status during gynecologic laparoscopy: 1) degree of Trendelenburg tilt (25 – 30°), 2) CO2 absorption and 3) increased intra-abdominal pressure (10 –20 mmHg). Slight modifications to any or all of these three factors can lead to a significant decrease in morbidity.

The AirSeal® valveless trocar system reduces CO2 absorption when compared to standard trocars during renal laparoscopy.¹ Also, use of this trocar system provides a more stable intra-abdominal pressure when compared to standard trocars, a feature that could possibly allow for laparoscopic surgery to be performed at lower intra-abdominal pressures.² We hypothesize that with the AirSeal® valveless trocar system, gynecologic laparoscopy can be performed at a lower intra-abdominal pressure with a possible resultant decrease in CO2 absorption, while maintaining adequate visualization of the operative field for safe completion of surgery.

The purpose of this study is to compare CO2 absorption during gynecologic laparoscopy using the AirSeal® valveless trocar system versus standard insufflation trocars at intra-abdominal pressures of 10 and 15 mmHg.

1.0 STUDY PURPOSE AND RATIONALE

Conventional and robotic-assisted laparoscopic procedures have become increasingly favored by gynecologists and their patients worldwide. As these minimally invasive techniques become more widespread, the surgeon has to be aware of, and respond to, different factors that will affect a patient's cardiopulmonary status during the procedure.

Three main factors affect patients' cardiopulmonary status during gynecologic laparoscopy.

During standard gynecologic laparoscopy, a 25-30° Trendelenburg tilt is needed to visualize the pelvic anatomy. In addition, an intra-abdominal pressure (IAP) of 10 to 20 mmHg is maintained with a continuous infusion of CO2 at a flow rate of 40L/min. The Trendelenburg tilt causes cardiovascular and gas exchange impairments that are exaggerated by the CO2 pneumoperitoneum.³ These factors affect the anesthesiologists' ability to ventilate the patient and maintain adequate end-tidal CO2 (ETCO2). Furthermore, CO2 which is the most commonly used gas for laparoscopy is absorbed transperitoneally and this absorption combined with hypercapnia and hypoventilation can lead to cardiac arrhythmias and even cardiac arrest.⁴ Multiple studies have demonstrated increased systemic absorption of CO2 gas during transperitoneal and retroperitoneal laparoscopy by measuring end-tidal CO2 (ETCO2) and CO2 elimination rates.^{5,6}

In attempts to minimize the effects of CO2 pneumoperitoneum, various modifications to traditional laparoscopy have been explored including gasless and/or low-pressure pneumoperitoneum, and use of alternate gases (nitrous oxide, argon, helium) for insufflation; all with varying degrees of success.^{7,8,9,10,11}

The AirSeal® valveless trocar system has the potential to minimize patient complications by decreasing systemic absorption of CO2 gas.

The AirSeal® valveless trocar system was designed to provide "stable pneumoperitoneum at a CO2 flow rate of 3L/min, continuous smoke evacuation and valve free access to the abdominal cavity"¹². Use of this system is also associated with a decrease in CO2 use, absorption and elimination when compared to standard trocars.¹ This reduction in CO2 absorption potentially makes the AirSeal® trocar system a more attractive alternative to standard insufflation. However to date, no randomized clinical trials have been performed to demonstrate clinically or statistically significant benefits of the AirSeal® trocar system until now.

The AirSeal® valveless trocar system has the potential to minimize patient complications by decreasing the intra-abdominal pressure needed to safely complete a laparoscopic gynecologic surgery.

There is scant evidence regarding the effect of low-pressure pneumoperitoneum on cardiopulmonary function during gynecologic laparoscopy. An increased intra-abdominal pressure during laparoscopic surgery reduces lung volume, increases peak airway pressure and decreases pulmonary compliance. In addition, this elevated pressure reduces diaphragmatic excursion and shifts the diaphragm cephalad, collapsing smaller airways and causing intraoperative atelectasis, which in turn decreases functional residual capacity.¹³ It therefore makes sense that, in the event of refractory hypoxemia, high peak pressures or hypercapnia, the recommendation by anesthesia is to release pneumoperitoneum and re-insufflate slowly using a lower intra-abdominal pressure.¹⁴ A recent systematic review of the use of low-pressure pneumoperitoneum revealed decreased pulmonary compliance in low-pressure vs. standard pressure pneumoperitoneum but showed comparable end tidal CO2, pCO2, oxygen saturation, pO2 and blood gas analyses.¹⁵ However, only one study in this review involved pelvic surgery and so the generalizability of these conclusions to gynecology is limited.

AirSeal® /CO2 absorption study protocol

Use of the AirSeal® trocar system provides a more stable intra-abdominal pressure when compared to standard trocars; a feature that could possibly allow for laparoscopic surgery to be performed at lower intra-abdominal pressures. We hypothesize that with the AirSeal® valveless trocar system, gynecologic laparoscopy can be performed at a lower intra-abdominal pressure with a possible resultant decrease in CO2 absorption, while maintaining adequate visualization of the operative field for safe completion of surgery. The purpose of this study

is to compare CO2 absorption during gynecologic laparoscopy using the AirSeal® valveless trocar system versus standard insufflation trocars at intra-abdominal pressures of 10 and 15 mmHg.

2.0 STUDY DESIGN AND STATISTICAL PROCEDURES

2.1 Overall design

Type of study: A randomized controlled trial

Randomization and blinding: Simple randomization

Single vs. multi-center: Single center

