2.4 Data Management and Analysis

In this study, the primary objective is to analyze the effect of two independent factors: 1. Type of trocar system (AirSeal® trocar vs. standard trocars) 2. Intra-abdominal pressure (IAP: 10 vs. 15 mmHg) on the dependent factor: CO2 absorption. This will result in four (4) study arms. CO2 absorption in each arm will be compared at 15 and 60 minutes.

Justification of sample size: An effect size of 0.46 was calculated based on average CO2 absorption rates in a study comparing CO2 absorption when using the AirSeal® trocar versus standard trocars for laparoscopic renal surgery.¹ 30 patients per arm would be needed to detect an effect size of 0.46 or greater, with 80% power and a two-tailed alpha of 0.01. In order to allow for a possible 10% drop out, 132 patients will be enrolled in the study.

CO2 absorption calculation:

CO2 elimination rate = CO²³ absorption rate in order to keep patient metabolically constant.

¹ Wolf JS Jr, Monk TG, McDougall EM, et al. The extraperitoneal approach and subcutaneous emphysema are associated with greater absorption of carbon dioxide during laparoscopic renal surgery. J Urol. 1995;154:959-963.

² Ng CS, Gill IS, Sung GT, et al. Retroperitoneoscopic surgery is not associated with increased carbon dioxide absorption. J Urol. ³ 162:1268-1272

V3 022417

^{1,2}

$$\text{Carbon dioxide elimination rate} = \frac{ETCO_2 \times Vt \times RR}{(P_B - P_{H2O}) \times Wt}$$

ETCO₂: end-tidal carbon-dioxide pressure, Vt: expired tidal volume, RR: respiratory rate, P_B: barometric pressure (760 mmHg), P_{H2O}: partial pressure of water (13 mmHg), Wt: patient's weight in kilograms

General Analyses

Continuous variables will be summarized using means, standard deviations, medians, and ranges. If normally distributed, they will be analyzed using parametric tests such as T-test and analysis of variance. To find associations between continuous variables and to control by relevant covariates we will use multiple regressions. If the normality assumption is violated we will use non-parametric tests such as Mann-Whitney or Kruskal-Wallis.

[figure not shown]
Categorical variables will be summarized with frequencies and percentages and analyzed with logistic regression or categorical response models.

95% confidence intervals will be provided for descriptive statistics, as warranted.

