2.5 Graphical schema of study

3.0 STUDY PROCEDURES

- . / In the pre-operative area, subjects will be randomized via sealed, opaque envelopes containing a simple randomization scheme to one of the four groups:
 - Group A: Standard trocar/IAP 15 mmHg
 - Group B: Standard trocar/IAP 10 mmHg
 - Group C: AirSeal® trocar /IAP 15 mmHg
 - Group D: AirSeal® trocar /IAP 10 mmHg
- . / All intraoperative staff assigned to the patient will be made aware of her participation in the study. The delegated research staff will fill out all pre-operative data. (CRF1)
- . / Once in the operating room, standard surgical positioning, prepping and draping will be performed.
- . / The patient's randomization group will be stated at the surgical TIME OUT.
- . / Proposed surgery will commence using the AirSeal® or standard trocar at IAP of either 10 or 15 mmHg.
- . / All cases will be performed with routine general endotracheal anesthesia. Ventilatory parameters and settings will be at the discretion of the anesthesiologists.
- . / Pneumoperitoneum will be established using the Veress needle and trocar insertion performed at 20 mmHg.
- . / Immediately following trocar insertion/port placement, pressure will be decreased to 10 or 15 mmHg.
- . / If at any point the surgeon or anesthesiologist feels that the patient's safety is in question, necessary changes, including increasing the intra-abdominal pressure or switching between trocars, will be made expeditiously, and recorded.
- . / During surgery, "surgical data" and "anesthesia data" variables will be filled. (CRF 3 & 4)
- . / Following surgery 'General intraoperative data' variables listed below will be collected. (CRF 2)
- . / At the end of the case, the surgeon and the anesthesiologist will complete questionnaires (CRF 3 & 4)
- . / Post-operatively, the patient will fill out Visual Analog Scale pain scores at specified time periods. (CRF 5)
- . / PACU/nursing staff will fill out a questionnaire indicating pain medication used during recovery and post-operative recovery time (CRF 6)

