8.0 INFORMED CONSENT PROCESS

After the provider determines eligibility of study participants, the informed consent process will be completed in 2 possible ways as listed/explained below by the PI or research staff (Co-investigator or other delegated study staff):

Option 1:

- . / Patient will be offered participation in the study at their pre-operative visit
- . / During this visit, the informed consent and HIPAA form will be explained and all questions answered
- . / The provider will inform the patient that participation in the study will be contingent on availability of the medical device on the day of the procedure
- . / The informed consent and HIPAA form will be signed by the patient and a copy given to them for their personal records
- . / The original 'wet-ink' signed consent and HIPAA form will be stored in the patient's chart
- . / On the procedure day, when the patient is in the pre-operative area, availability of the medical device will be confirmed and then the patient will be randomized into 1 of 4 groups
- . / Patients who are consented but not randomized will not be considered 'drop outs'

Option 2:

- . / At the time of the pre-operative visit, if time does not permit for consent to be obtained, the provider will obtain permission from the patient to allow a member of research team contact them about an ongoing research study – if the provider is not a Co-I in the study, he/she will document permission for the research team to contact the subject
- . / The patient will be given a copy of the informed consent and HIPAA form with their pre-operative packet and asked to review it in anticipation of a call (if they have agreed to this).
- . / A member of the research team will contact the patient to review the informed consent and HIPAA form and answer all questions
- . / Patient will be informed that participation in study will be contingent on availability of the medical device on the day of the procedure
- . / At the end of the phone conversation patient consent (or denial of consent) will be obtained and documented in patient's chart
- . / If the patient consents to participate by telephone, their signature will be obtained on the consent form in the preoperative area
- . / A copy of the signed form will be given to the patient and the original 'wet-ink' copy will be stored in the patient's chart
- . / When availability of the medical device is confirmed the patient will be randomized into 1 of 4 groups

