- . / Patients who are consented but not randomized will not be considered 'drop outs'

With both options of the informed consent process, when participation is offered to the patient, the informed consent and HIPAA form will be explained in detail along with the study design, procedures, inclusion/exclusion

criteria, risks and benefits, and study requirement. It will be emphasized that participation is completely voluntary and that she may revoke her participation at any time. There will be no further documentation of the informed consent process.

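### Does simple randomization to four arms, with no control of arm size, weaken the trial enough to count as a fault?

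*Combined protocol and SAP*

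**What the plan says.** Section 2.1 gives the allocation method as "Randomization and blinding: Simple randomization". Section 3.0 says that patients are allocated in the pre-operative area by "sealed, opaque envelopes containing a simple randomization scheme to one of the four groups". Neither section mentions blocks, strata or any other limit on arm size.

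Section 2.4 sets the sample size by arm: "30 patients per arm would be needed to detect an effect size of 0.46 or greater", at 80% power and a two-sided level of 0.01. Enrolment is raised to 132 for 10% drop-out. The same section says that "CO2 absorption in each arm will be compared at 15 and 60 minutes". Hypotheses 1a and 1b in section 2.3 are each about one factor: trocar type and pressure.

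Other passages bear on how guessable an allocation would be and whether anyone could act on a guess:

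- Section 3.0: the "randomization group will be stated at the surgical TIME OUT", so the operating team knows it.
- Section 7.0: the recruiting providers are all co-investigators.
- Section 8.0: on the day of surgery, "availability of the medical device will be confirmed and then the patient will be randomized into 1 of 4 groups". Patients who consented but were never randomized do not count as drop-outs.
- Section 8.0, Option 2: "If the patient consents to participate by telephone, their signature will be obtained on the consent form in the preoperative area".

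**The concern.** The sample size is fixed per arm, yet the allocation method leaves the number per arm to chance. With four arms and 132 patients the imbalance is visible: the largest and smallest arms differ by about 12 patients on average, and in about 79% of allocation lists at least one arm is randomized fewer than 30. An arm of 25 or fewer occurs in about 25% of lists. Permuted blocks would hold the arms almost equal at the cost of a new list in the same envelopes. If the loss of precision were large, the stated 80% power would be overstated for some comparisons, and a standard device would have been left out for no reason.

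**Working it through.** **Inputs.** From section 2.4: 30 per arm, effect size 0.46, 80% power, two-sided alpha 0.01, 10% drop-out, 132 enrolled. Assumed: allocation probability 1/4 per arm, and drop-out independent of arm and outcome. The plan does not say which effect-size metric 0.46 is, so the results are given for more than one reading.

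**The plan's own figure.** Read 0.46 as Cohen's f for two groups, so d = 2 × 0.46 = 0.92.

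- Normal approximation: n = 2(2.576 + 0.842)² / 0.92² = 27.6, or 28 per arm.
- Noncentral t: 29.3, or 30 per arm, with power 81.2% at 30 v 30.
- Enrolment: 4 × 30 = 120, and 120 × 1.10 = 132.

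This reproduces the plan. The other readings tried do not: d = 0.46 needs about 112 per arm, and f = 0.46 in a four-group analysis of variance needs 79 in total.

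**Spread of arm sizes.** For one arm, SD = √(132 × 0.25 × 0.75) = 4.97 around 33. With varied blocks of 8 and 12 the simulated SD is 0.55, and the mean gap between largest and smallest arm is 1.0 instead of 11.8.

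**Loss of precision, by hand.** After drop-out the mean arm size is 132 × 0.25 × 0.9 = 29.7. The mean of 1/n is approximately (1/29.7)(1 + CV²), where CV² is the variance of n divided by its squared mean.

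- Simple: variance 132 × 0.225 × 0.775 = 23.02, so CV² = 23.02 / 29.7² = 0.0261.
- Equal arms of 33 before drop-out: variance 33 × 0.9 × 0.1 = 2.97, so CV² = 0.0034.
- Ratio: 1.0261 / 1.0034 = 1.023.

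Simulation of the main-effect variance, Σ(1/n)/4, gives 0.0346 v 0.0338, a ratio of 1.024. That is worth 0.024 × 119 = 2.9, or about 3 of some 119 evaluable patients.

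**Power after drop-out, two-sided alpha 0.01.**

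| Comparison and reading of 0.46 | Simple | Blocks of 8 and 12 |
|---|---|---|
| Two arms, d = 0.92: mean | 79.4% | 80.5% |
| Two arms, d = 0.92: 5th percentile over lists | 70% | 77% |
| Main effect, d = 0.92 | 98.9% | 99.1% |
| Two arms, d = 0.46 | 19.3% | 19.6% |
| Main effect, d = 0.46 | 44.5% | 45.7% |

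If 0.46 is a four-group f, overall power is 95.3% to 95.9% under simple randomization, depending on the pattern of means, against 96.1% with equal arms.

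**What blocking costs.** Take an observer who knows all past allocations and always guesses the least-used arm.

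| Scheme | Arm guessed correctly | Trocar type guessed correctly |
|---|---|---|
| Simple | 25% | 50% |
| Blocks of 8 and 12 | 45% | 65% |
| Blocks of 4 and 8 | 49% | 68% |
| One shuffled list of 132 | 32% | 55% |

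**How a guess could become bias (illustration; the size of selection is an assumption).** Suppose the patients randomized differ by ±η SD in expected outcome according to the guessed trocar. At 65% correct guesses each trocar group's mean shifts by (0.65 − 0.35)η = 0.3η in opposite directions, so the contrast is biased by 0.6η. Its standard error with 119 patients is 2/√119 = 0.183 SD.

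- η = 0.1: shift 0.06 / 0.183 = 0.33 standard errors; type I error rises from 1.0% to about 1.4%.
- η = 0.2: shift 0.12 / 0.183 = 0.65 standard errors; type I error rises to about 2.8%.

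Under simple randomization this bias is zero.

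**The case for a change.** The strongest case for blocking is that averages hide what a single trial may meet. Section 2.4 compares arms, so the two smallest arms will form one of the pairs. At d = 0.92 the power for that pair averages 73.0% under simple randomization and 78.5% with blocks of 8 and 12 (5th percentiles 65% and 75%). The remedy needs no extra patients, and d = 0.92 is the only reading tried that returns the plan's 30 per arm.

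The room to act on a guess is also limited. Consent usually precedes the day of surgery, the device check comes before randomization, and nothing in the documents suggests that anyone would track allocations. The bias illustration is therefore an upper-end case. A single shuffled list of 132 would give equal arms at full enrolment with a lower guess rate. Its limits are that the last 12 allocations are guessed correctly about 51% of the time, and that balance is weaker if enrolment stops early (arm SD 2.1 at 100 patients, against 4.3 for simple randomization and 0.55 for blocks).

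All of this stands as an argument for preferring a restricted scheme; none of it shows an error. The worst-pair figure selects the least favourable of six pairs after the fact, whereas Hypotheses 1a and 1b use all four arms and lose almost nothing. The opportunity for selection is small but present: under telephone consent the signature is taken on the day, and patients not randomized leave the drop-out count. Section 3.0 already has sealed opaque envelopes, and section 8.0 already places randomization after consent and the device check. How the list is generated and whether envelopes are numbered are not described, but those are missing details under any scheme and do not count against simple randomization.

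**Conclusion.** The concern does not hold. Sections 2.1 and 3.0 agree, simple randomization is valid and unbiased, and no stated rule or promised arm size is broken. The cost is precision only: on average 1.1 points of power for a pair of arms and 0.2 point for each main effect if 0.46 means d = 0.92; 0.3 and 1.2 points if it means d = 0.46. In the second case power is about 20% and 45% under either scheme, so arm balance is not what limits it. In return, the allocation cannot be predicted in an open, single-centre trial run by its own recruiters. Reasonable statisticians would differ on this exchange, and keeping simple randomization is a defensible side of it.

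These figures rest on equal allocation probabilities, 132 randomized, independent 10% drop-out and a two-sided level of 0.01. The conclusion is the same under every reading of 0.46 that was tried.

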2.2 Study objectives

2.2.1 Primary objective: To compare CO2 absorption during gynecologic laparoscopy using the AirSeal® valveless trocar system versus standard insufflation trocars at intra-abdominal pressures of 10 and 15mmHg

2.2.2 Secondary objectives:

a) To evaluate the anesthesiologists' perception of difficulty in maintaining adequate ETCO2 during laparoscopy using the AirSeal® valveless trocar system versus standard insufflation trocars at intra-abdominal pressures of 10 and 15mmHg

b) To evaluate the surgeon's visualization of the operative field during laparoscopy using the AirSeal® valveless trocar system versus standard insufflation trocars at intra-abdominal pressures of 10 and 15 mmHg

c) To compare post-operative shoulder-tip pain when using the AirSeal® valveless trocar system versus standard insufflation trocars at intra-abdominal pressures of 10 and 15 mmHg

2.3 Aims & Hypotheses

2.3a Specific Aim 1

To determine if there is a difference in CO2 absorption when gynecologic laparoscopy is performed using the AirSeal® valveless trocar system versus standard insufflation trocars at intra-abdominal pressures of 10 and 15mmHg

2.3a.1a Hypothesis 1a

CO2 absorption is decreased when gynecologic laparoscopy is performed using the AirSeal® valveless trocar system versus standard insufflation trocars

2.3a.1b Hypothesis 1b

CO2 absorption is decreased when gynecologic laparoscopy is performed at an intra-abdominal pressure of 10 versus 15 mmHg

2.3b Specific Aim 2

To determine if the anesthesiologists' perception of difficulty in maintaining adequate ETCO2 during gynecologic laparoscopy as measured on a 3-point likert scale differs using the AirSeal® valveless trocar system versus standard insufflation trocars at intra-abdominal pressures of 10 and 15mmHg

2.3b.1 Hypothesis 2

Maintaining adequate ETCO2 is less challenging when using the AirSeal® valveless trocar system versus standard insufflation trocars for gynecologic laparoscopy at intra-abdominal pressures of 10 and 15 mmHg

2.3c Specific Aim 3

To determine if the surgeon's visualization of the operative field during gynecologic laparoscopy as measured on a visual analog scale (VAS) differs when using the AirSeal® valveless trocar system versus standard insufflation trocars at intra-abdominal pressures of 10 and 15 mmHg

2.3c.1 Hypothesis 3

Visualization of the operative field is improved when using the AirSeal® valveless trocar system versus standard insufflation trocars for gynecologic laparoscopy at intra-abdominal pressures of 10 and 15 mmHg

2.3d Specific Aim 4

To determine if post-operative shoulder pain as measured on a VAS pain scale differs following gynecologic laparoscopy using the AirSeal® valveless trocar system versus standard insufflation trocars at intra-abdominal pressures of 10 and 15 mmHg

2.3d.1 Hypothesis 4

Post-operative shoulder pain is improved following gynecologic laparoscopy using the AirSeal® valveless trocar system versus standard insufflation trocars at intra-abdominal pressures of 10 and 15 mmHg

